6.12.8.2.1. Analyses of Characteristics of ADA Immune Response

The analyses of ADA effects will be conducted on all evaluable patients within the defined Safety Population for Blinded Treatment Dosing Period (Period 2), and Combined Blinded Treatment Dosing and Extended Treatment Periods (Combined Periods 2 and 3).

Baseline definition for immunogenicity analyses for the Combined Treatment Period is the same as [Table RHBV.6.10](#).

The overall frequency and percentage (incidence) of patients will be summarized for the TE-ADA status groups and the time-varying TE-ADA status groups. Scheduled visits, unscheduled visits, and repeat measurements will be included.

In addition, the overall frequency and percentage (incidence) of patients will be summarized for the patients who are baseline ADA positive by TE-ADA status groups. For those patients who are TE-ADA positive, a summary of titer values and the proportion of patients who are NAb positive will also be provided.

The time to the development of TE-ADAs (TE-ADA positive, low titer, moderate titer, high titer, and NAb positive) will be calculated as follows:

Time to development of TE-ADAs/NAb (in weeks) = (Date of development of TE-ADAs/NAb – Date of first injection of study treatment + 1) / 7.

If a patient has not developed TE-ADAs/NAbs, they will be censored at the date of the last immunogenicity assessment.

Descriptive statistics, including 25th percentile, 50th percentile (median), 75th percentile, and corresponding 95% CIs as well as proportion of TE-ADA/NAb positive by endpoint summarized by treatment group, will also be provided if sufficient data is present. A Kaplan-Meier plot of the time to development of treatment-emergent ADA/NAb will be presented by treatment group, also if sufficient data is present.

For each TE-ADA status dichotomous variable (as defined in [Table RHBV.6.11](#)), summaries will be provided of the total postbaseline time in the greater-TE-ADA status for patients who were at some point postbaseline in the greater-TE-ADA status group. Postbaseline time in greater-TE-ADA status for each patient will be aggregated.

A by-patient listing to include treatment, visit date, visit, ADA result, TE-ADA result, NAb result, ADA titer value, ixekizumab concentration, ADA and NAb inconclusive results will also be provided, for patients with any one sample of ADA (or NAb) positive or inconclusive.

6.12.8.2.2. Analyses of ADA Effects on Efficacy

Efficacy analyses for Period 2 and Period 3 will be conducted on all evaluable patients within the ITT Population and Extended Treatment Period Population.

The ASAS40, ASAS20 and ASDAS inactive disease at week 16 with NRI will be summarized by the TE-ADA status groups as described in [Section 6.12.8.2](#).

A logistic regression model with treatment group, TE-ADA status group (excluding patients in the TE-ADA inconclusive category for TE-ADA, excluding TE-ADA positive and co-occurring NAb inconclusive subgroups for NAb), and the interaction of treatment group-by-TE-ADA status group included as factors will be used to test the interaction of treatment group-by-TE-ADA status group for ITT Population during Period 2. The p-value associated with the

interaction term will be used to assess if the treatment groups effect is consistent across the TE-ADA status group. When the interaction term is statistically significant, the association between responder status and treatment depends, in some manner, on the TE-ADA status group. The interaction will be tested at the 10% significance level. Treatment differences will be evaluated within each subgroup using Fisher's exact test regardless of whether the interaction is statistically significant.

Response rates for ASAS40, ASAS20, and ASDAS inactive disease at Week 16 will be provided and compared among the TE-ADA status (and TE-ADA tiers) and NAb status groups for the ITT Population who were treated with Ixekizumab.

Descriptive statistics for ASAS40 and ASAS20 at Week 52 based on the TE-ADA status (and TE-ADA tiers) and NAb status group will be provided for the Extended Treatment Period Population. No inferential statistics will be performed.

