6.10.1. Primary Outcome and Methodology

The primary outcome is the proportion of patients achieving ASAS40 at Week 16 (Visit 8). This is a de-facto (effectiveness) estimand (that is, the effect attributable to the originally randomized treatment, ixekizumab, adalimumab and placebo, at the primary time point of Week 16 in all randomized patients).

The primary outcome related to improvement in symptomatic feature of AxSpA are assessed at Week 16 (Visit 8) prior to adalimumab and placebo patients being rerandomized to ixekizumab during Period 3 (Extended Treatment Period).

The primary analysis will be based on the ITT Population for the Blinded Treatment Dosing Period (Period 2) comparing each ixekizumab treatment group and placebo at Week 16 (Visit 8). The primary analysis is a logistic regression analysis with treatment, geographic region, and baseline CRP status in the model (Section 6.1.1).

In the primary analysis, treatment groups of ixekizumab 80 mg Q2W and Q4W will be analyzed without regard to starting dose. The primary comparison will be tested based on the graphical multiple testing procedures detailed in Section 6.5.

Table RHBV.6.5 provides the detailed analyses including analysis type, method and imputation, population, time point, and treatment comparisons for primary outcome.

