6.12.8.1.3. Definitions for Clinical Interpretation of Assay Results

- Baseline:** For immunogenicity analyses during Period 2, baseline is the last nonmissing observation on, or prior to, the date of the first injection of study treatment (Week 0). Unless otherwise specified, the baseline for Period 3 is defined as the last non-missing observation on, or prior to, the date of first injection of ixekizumab. For patients originally randomized to ixekizumab during Period 2, baseline is the last non-missing observation on, or prior to, the date of the first injection of study treatment for Period 2 (Week 0). For patients who are not originally randomized to ixekizumab in Period 2, baseline is the last non-missing observation on, or prior to, the date of the first injection of ixekizumab. See [Table RHBV.6.10](#) for further details.

[figure not shown]
Table RHBV.6.10. Baseline Definition for Immunogenicity Analyses for Extended Treatment Period

Treatment Assignment for Blinded Treatment Dosing Period (Period 2)	Treatment Assignment for Extended Treatment Period (Period 3)	Baseline for Extended Treatment Period Analysis ^a
Ixekizumab	Ixekizumab	Week 0
Adalimumab	Ixekizumab	Week 20
Placebo	Ixekizumab	Week 16

^a Last non-missing observation on, or prior to, the date of the first injection of study treatment at the defined week.

- **Baseline ADA positive (preexisting antibody):** ADA detected in a sample collected at baseline.
- **Baseline ADA-negative:** ADA is not detected in a sample collected at baseline.
- **TE-ADA positive:** a) a patient with a ≥ 4 -fold increase over a positive baseline antibody titer (Tier 3); or b) for a negative baseline titer, a patient with an increase from the baseline to a level of $\geq 1:10$.
- **TE-ADA inconclusive patient:** A patient without a TE-ADA positive sample and with at least one sample for which drug levels may interfere with the ADA assay.
- **TE-ADA negative patient:** A patient who is evaluable for TE-ADA and is not either TE-ADA positive or TE-ADA inconclusive.

Figure RHBV.6.6 illustrates the relationship of some of these terms.

Abbreviation: ADA = anti-drug antibody.

[figure not shown]
Figure RHBV.6.6. Relationship of terms for clinical interpretation of assay results for evaluable patients.

- **Incidence of TE-ADA:** Patients with TE-ADA as a proportion of the evaluable patient population during the treatment period. This excludes unevaluable patients.

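### The Period 2 treatment-by-TE-ADA interaction (SAP 6.12.8.2.2) cannot support its stated conclusion of a consistent effect versus placebo, because anti-ixekizumab antibody should be absent or rare in both control arms at Week 16

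*SAP*

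**What the plan says.** SAP 6.12.8.2.2 sets the population broadly: "Efficacy analyses for Period 2 and Period 3 will be conducted on all evaluable patients within the ITT Population" and the Extended Treatment Period Population. For Period 2 it fits treatment, TE-ADA status and their interaction, leaving out TE-ADA-inconclusive patients (and, for the neutralizing-antibody (NAb) version, NAb-inconclusive positives). This model "will be used to test the interaction of treatment group-by-TE-ADA status group for ITT Population during Period 2". The p-value for the "interaction term will be used to assess if the treatment groups effect is consistent across the TE-ADA status group". "The interaction will be tested at the 10% significance level", and whatever it shows, "Treatment differences will be evaluated within each subgroup using" Fisher's exact test.

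The section names no arms for this model. SAP 6.1.5 defines ITT as everyone randomized, and Table RHBV.6.2 makes the Period 2 ITT comparisons against placebo. Where the SAP wants ixekizumab arms only, it says so: the starting-dose models in 6.1.1 are limited that way, and so is the next comparison in 6.12.8.2.2, made by TE-ADA and "NAb status groups for the ITT Population who were treated with Ixekizumab".

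Three other places fix the timing and the antibody:
- SAP 6.10.1: the Week 16 primary outcomes "are assessed at Week 16 (Visit 8) prior to adalimumab and placebo patients being rerandomized to ixekizumab". Protocol 4.3 starts ixekizumab at Week 20 in the adalimumab arm.
- Protocol Appendix 3 lists the immunogenicity test as anti-ixekizumab antibody.
- SAP 6.12.8.1.3: "For immunogenicity analyses during Period 2, baseline is the last nonmissing observation on, or prior to" the first Week 0 injection. Positivity is a titre rule with no exposure condition.

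**The concern.** To learn whether the effect versus placebo holds up in antibody-positive patients, one needs positive patients on placebo. Patients never exposed to ixekizumab should rarely meet a treatment-emergent rule for antibody to it. Without them, the placebo-by-status term cannot be estimated, and what remains of the interaction is whether TE-ADA status relates to response differently under Q2W and Q4W. That is not the question the p-value is assigned.

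The risk is misreading in either direction. Antibodies could remove response equally in both regimens and leave the interaction non-significant, which a report could present as an effect that is consistent regardless of antibodies. A difference between regimens could equally be read as loss of effect versus placebo.

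The within-stratum Fisher tests share the problem. Among positives there may be no comparator. Among negatives, ixekizumab patients selected on a post-randomization result are compared with nearly all controls, so randomization no longer protects the contrast. NAb status is defined only for TE-ADA-positive patients (SAP 6.12.8.2), so the NAb version has the same gap.

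**Working it through.** **Inputs.** From SAP 5.3: 80 patients per arm, and ASAS40 response of 44% on Q2W and 16% on placebo. From SAP 6.12.8.2.2: interaction level 0.10. The documents give no TE-ADA rate, no false-positive rate and no power for this test, so there is no plan figure to reproduce and every antibody count below is an assumption.

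**1. No control positives.** Assume Q2W has 4/12 responders among positives and 31/68 among negatives, and Q4W 1/8 and 33/72. With adalimumab at 29/80 and placebo responders set in turn to 5, 13 and 40 of 80, the four-arm likelihood-ratio (LR) interaction is 1.102 on 1 df, p = 0.294, every time. The ixekizumab-only model gives the same 1.102 and 0.294. Placebo data have no influence, and the positive-stratum Fisher test against placebo has an empty row.

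**2. Rejection rates.** Assume 12 positives per ixekizumab arm (15%), response 44% in ixekizumab negatives and 16% in ixekizumab positives (effect wholly lost), placebo 16%, and no adalimumab positives. Over 1,500 simulated trials, the LR test at 0.10 rejects as follows:

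| Placebo positives | 0 | 1 | 2 | 4 | 8 |
|---|---|---|---|---|---|
| Rejection rate | 15% | 19% | 18% | 22% | 29% |

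With no placebo positives the regimens do not truly differ, so 15% is only the small-sample false-positive rate of a nominal 10% test.

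**3. Which test is used.** Assume 8 positives and 72 negatives per ixekizumab arm, negatives responding 32/72. Controls respond 13/79 (placebo) and 30/79 (adalimumab) among negatives, with one non-responding positive in each control arm. A 0/1 cell adds a degree of freedom and, at convergence, nothing to the Wald statistic, which is then the Q4W-versus-Q2W contrast alone. With a and b positive responders on Q4W and Q2W:

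W = [ln(a/(8−a)) − ln(b/(8−b))]² / [1/a + 1/(8−a) + 1/b + 1/(8−b) + 2(1/32 + 1/40)]

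At a = 1, b = 6 the numerator is (−1.946 − 1.099)² = 9.27, the denominator is 1 + 0.143 + 0.167 + 0.5 + 0.1125 = 1.922, and W = 4.82.

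| Q4W, Q2W positive responders | Wald p, 1 df (no control positives) | Wald p, 3 df | LR p, 3 df |
|---|---|---|---|
| 1/8, 1/8 | 1 | ≥0.999 | 0.97 |
| 3/8, 3/8 | 1 | ≥0.999 | 0.81 |
| 1/8, 6/8 | 0.028 | 0.185 | 0.058 |
| 1/8, 7/8 | 0.012 | 0.097 | 0.014 |

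At 1/8 and 6/8, Wald and LR fall on opposite sides of 0.10. At 1/8 and 1/8 neither sees anything, while pooling the ixekizumab arms gives 2/16 responders among positives against 64/144 among negatives, Fisher p = 0.015.

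**4. Fisher in the positive stratum.** With one placebo positive and 4, 8 or 12 ixekizumab positives, the smallest attainable two-sided p is 0.200, 0.111 or 0.077. Power at 0.05 for 44% versus 16% is at most 0.12% with two placebo positives and at most 1.9% with four.

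**5. How often the placebo-positive cell is unusable.** At assumed false-positive rates of 0.5%, 1%, 2% and 5%, the chance of no positive among 80, (1 − r)^80, is 0.67, 0.45, 0.20 and 0.02. Adding the case where all placebo positives respond or none does (16% response), the cell is empty or separated with probability 0.98, 0.94, 0.83 and 0.54.

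**The case against.** The strongest reply is that the missing arm restriction is not the cause. That stands: step 1 gives the same p-value with and without the control arms. The cause is scarce positivity off ixekizumab.

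A reader might also infer that the test can only ever compare regimens, or that a control positive can only be an assay artefact. The documents do not support either. Positivity is defined by titre alone, every patient is sampled (Protocol 8.4.9), and the SAP recognises pre-existing antibody. Any placebo positive brings placebo data in, and one that responds changes the picture: at 1/8 and 1/8 with one adalimumab positive not responding, the LR p falls from 0.97 to 0.089. Protocol 8.8.1 also allows antibodies to active comparators to be assessed; the laboratory list, and the SAP's use of ixekizumab concentration to confirm negative results, still make the ixekizumab reading the likelier one.

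A further tempting claim is that stray control positives dilute the regimen contrast past the 10% threshold. That holds for Wald at 1/8 and 6/8 (0.028 becomes 0.185) but not for LR (0.058). SAP 6.1.1 specifies Wald for the main logistic comparisons; 6.12.8.2.2 names no statistic. One non-responding positive in each control arm is itself only one of many possible configurations.

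Finally, the analysis is supportive and unadjusted, no decision rule uses it, and the protocol objective (response by TE-ADA and NAb status) is met by the ixekizumab-only comparison. All of that limits the weight of the point. None of it makes the stated use of the p-value valid.

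**Conclusion.** The rule should be changed, though it is not critical. With no control positives, the interaction says nothing about consistency versus placebo. With a few, it says very little (18% to 22% rejection with one to four placebo positives when the effect is entirely lost, against 15% with none), and the answer can turn on the choice of test. The SAP gives no help with sparse cells here: the 6.1.1 fallback to Fisher does not test an interaction, and the rule in 6.14.1 for subgroups under 10% is not carried into this section.

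The direction of the conclusion follows from exposure timing. The sizes rest on assumed antibody counts and on the SAP 5.3 response rates. Restricting the model does not by itself detect an equal loss of response in both regimens: at 1/8 and 1/8 the restricted interaction also gives p = 1. The pooled ixekizumab comparison by status does detect it (p = 0.015 at those counts). Nothing here touches the primary or major secondary results.

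**What to change.** 1. Limit the interaction model to the two ixekizumab arms and state that it compares regimens, or drop it. In either case, remove the use of its p-value as evidence of consistency versus placebo.
2. Do not interpret the within-stratum Fisher tests against placebo or adalimumab. If they have already been produced, show them with cell counts and label them non-estimable or uninterpretable, rather than deleting them silently.
3. Make the ixekizumab-only comparison by TE-ADA and NAb status, already in 6.12.8.2.2, the main analysis of antibody effect on efficacy, described as a non-randomized comparison by post-baseline status.
4. Record the change and its reason. SAP Version 3 was approved after unblinding, and its only logged change to 6.12.8 removes ASDAS inactive disease from the Week 52 analyses, so the log indicates that the interaction was planned before unblinding. The change should be disclosed as made after unblinding and justified by exposure timing, not by results.

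The cost is one SAP paragraph, labels on any existing outputs and a change record. No new data are needed.

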6.12.8.2.3. Analyses of Treatment-Emergent ADA on Specific Adverse Events

The analyses of TE-ADA effects on safety will be conducted on all evaluable patients within the defined Safety Population for Blinded Treatment Dosing Period (Period 2) and Combined Blinded Treatment Dosing and Extended Treatment Periods (Combined Periods 2 and 3).

Baseline definition for immunogenicity analyses for the Combined Treatment Period is the same as [Table RHBV.6.10](#).

AESIs of allergic reaction/hypersensitivity (anaphylaxis and non-anaphylaxis) and of injection-site reactions will be included in an assessment of AE to TE-ADA over time. Timing of an AE will be taken to be the reported AE start date.

For each TE-ADA status dichotomous variable (as defined in [Table RHBV.6.11](#)), patients will be categorized according to whether they were (i) always in lesser-TE-ADA status postbaseline or (ii) at some point postbaseline, were in greater-TE-ADA status. For each AESI, within the time-varying TE-ADA status groups, a summary will be provided of the number of patients who had no event, events only while in lesser-TE-ADA status for group (i), or – for group (ii) – at least one event while in greater-TE-ADA status.

Additionally, summaries will be provided of the total number of AESI events (with unique start dates) by time-varying TE-ADA status groups at the event date. The summaries will aggregate time respectively in greater-TE-ADA status and in lesser-TE-ADA status, along with the event rates (rates per 100 patient-years) relative to those aggregate times.

By-patient listings will be provided of patients with TE-ADA who experience a treatment-emergent allergic reaction/hypersensitivity reaction or an injection site reaction.

6.13. Analysis for Submission to Japan - Regulatory Body

A subset of the planned efficacy and safety analyses will be summarized based on patients from Asian sites (Japan, Korea, and Taiwan), in support of the regulatory submission in Japan. The list of tables, listings, and figures for the patients from Asian sites (Asian population) will be in a separate document.

In addition, a by-patient listing of patients from Asian sites with the number of self-injections will be provided for Period 2 and Period 3. The self-injection is defined as the injection administered either by study subject or by caregiver during Period 2 and Period 3, respectively.

6.14. Subgroup Analyses

6.14.1. Efficacy Subgroup Analyses

Subgroup analysis will be conducted for the primary endpoints of proportion of patients achieving an ASAS40 response at Week 16 (NRI) using the ITT Population for the Period 2. The major secondary efficacy endpoints, the proportion of patients achieving ASAS20 (NRI) and ASDAS inactive disease (NRI) at Week 16, will also be conducted.

For categorical response variables (ASAS20, ASAS40, and ASDAS inactive disease), a logistic regression analysis with treatment, subgroup, and treatment-by-subgroup interaction as factors will be used. The treatment-by-subgroup interaction will be tested at the 10% significance level. Treatment group differences will be evaluated within each subgroup using the Fisher's exact test, regardless of whether the interaction is statistically significant. If any group within the subgroup (for example, yes, no) is <10% of the total population, only descriptive statistics will be provided for that subgroup (that is, no inferential testing).

Forest plots may be created to illustrate the treatment differences with 95% CIs between each of the ixekizumab treatment groups and placebo group, by each subgroup category.

The following subgroups will be analyzed:

- Patient Demographics Subgroups:
 - Sex
 - Age category: <40 years, ≥40 years
 - Age category: <50 years, ≥50 years
 - Age category: <65 years, ≥65 years
 - Weight: <70 kg, ≥70 kg
 - BMI: underweight (<18.5 kg/m²); normal (≥18.5 and <25 kg/m²); overweight (≥25 and <30 kg/m²); obese (≥30 and <40 kg/m²); or extreme obese (≥40 kg/m²)
 - Ethnicity: Hispanic/Latino, Non-Hispanic/Non-Latino
 - Race: American Indian/Alaska Native, Asian, Black/African American, Native Hawaiian or other Pacific Islander, White, or Multiple
- Geographic Region Subgroups:
 - Geographic region: Europe, non-Europe
 - Geographic region: America, Asia, Europe
 - Geographic region: North America (US including Puerto Rico if any, Canada), rest of the World
 - Geographic region: US (including Puerto Rico if any), non-US
- Baseline Severity of Disease Subgroups:
 - Baseline CRP categories:
 - ≤3.00 mg/L or >3.00 mg/L

- ≤ 5.00 mg/L or > 5.00 mg/L
 - ≤ 10.00 mg/L or > 10.00 mg/L
 - ≤ 15.00 mg/L or > 15.00 mg/L
- Baseline MRI status:
 - SPARCC SIJ score ≥ 2 or < 2
 - SPARCC Spine score ≥ 2 or < 2
 - ASSpiMRI-Berlin score > 0 or $= 0$
- Other Patient Characteristics Subgroups:
 - Duration of symptom since AxSpA onset category: < 10 years or ≥ 10 years;
 - Duration of symptom since AxSpA onset category: < 5 years or ≥ 5 years;
 - Duration of symptom since AxSpA onset category: < 3 years or ≥ 3 years
 - HLA-B27 status: positive or negative
 - Smoking status: current or former/never
 - Concomitant cDMARDs (methotrexate, sulfasalazine, hydroxychloroquine) at baseline: yes or no
 - History of arthritis: yes or no
 - History of uveitis: yes or no
 - History of dactylitis: yes or no
 - History of psoriasis: yes or no
 - History of enthesitis: yes or no
 - History of inflammatory bowel disease: yes or no
 - History of extra-axial involvement: yes or no.

Additional subgroup analyses on efficacy may be performed as deemed appropriate and necessary.

6.14.2. Safety Subgroup Analyses

Safety subgroup analysis for common TEAEs and AESI of allergy reaction/hypersensitivity and infections will be summarized by treatment group and overall, using the Safety Population for the Period 2. The common TEAEs will be presented by MedDRA PT within SOC. The AESI of allergy reaction/hypersensitivity will be presented by anaphylaxis and non-anaphylaxis events, by PT within category. The AESI of infection will be presented by PT.

A logistic regression model with treatment, subgroup, and the interaction of subgroup-by-treatment included as factors will be used. The subgroup-by-treatment interaction will be tested at the significance level of 0.10. The response variable will be each AE. Treatment group differences will be evaluated within each category of the subgroup using Fisher's exact test, regardless of whether the interaction is statistically significant. If any group within the subgroup is less than 10% of the total population, only the descriptive statistics will be provided for that subgroup (that is, no inferential testing).

The subgroups include baseline demographics and geographic region, and are defined in Section [6.14.1](#).

Additional subgroup analyses on safety may be performed as deemed appropriate and necessary.

